5.2 Per Protocol Set

Per Protocol Set (PPS) will be a subset of FAS, excluding subjects who have major protocol deviations, which impact the primary endpoint evaluation. The per protocol set will be used for the sensitivity analyses of the primary endpoint.

5.3 Safety Analysis Set

The Safety Analysis Set will be the same as FAS. The safety analysis set will be the primary population for evaluating treatment administration, concomitant medication and safety.

6 GENERAL CONSIDERATIONS

6.1 Data Analysis Conventions

Statistical programming and analyses will be performed using SAS® Version 9.4 or higher.

Summaries for continuous and ordinal variables will include the number of observations (n), arithmetic mean, standard deviation (SD), median, minimum, and maximum. Minima and maxima will be reported with the same precision as the raw values; means and medians will be presented to one additional decimal place than reported in the raw values. Standard deviations will be presented to two additional decimal places than reported in the raw values.

Summaries for discrete variables will include counts and percentages. All percentages will be rounded to one decimal place.

All safety and efficacy summaries will be presented by treatment group and overall, where appropriate, for each study visit. Listings will be sorted by treatment group, subject number, study visit, and parameter, as applicable.

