Efficacy and Safety Assessments	
The efficacy evaluation will be based on measurements of BCVA (using ETDRS), ultrasonic contact pachymetry, [REDACTED], [REDACTED]
 
The safety evaluation will be based on adverse event (AE) reporting, laboratory findings (clinical chemistry and hematology), and ophthalmic examinations, including Goldmann tonometry, Slit Lamp biomicroscopy, gonioscopy, dilated fundoscopy, and BCVA (as measured by ETDRS).
 
All ocular assessments will be conducted on both eyes.

Sample Size Considerations	
This sample size is based on clinical feasibility and adequate size to characterize safety in the study population, without consideration for statistical power.

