AURN001 is a combination product of allogeneic human corneal endothelial cells (*neltependocel*) and a small molecule drug (Y-27632, a Rho-kinase inhibitor). AURN001's corneal endothelial cells are isolated from transplantation-grade corneas and expanded ex-vivo (Figure 1). The cells harvested for AURN001 express identity marker [REDACTED]

[REDACTED]
They also show the presence of [REDACTED]
[REDACTED]

The presence of Y-27632 in the formulation enhances the cells adhesion by promoting cytoskeletal changes. Furthermore, Y-27632 activates molecular pathways that promote cell survival during delivery to the recipient's cornea, increasing the likelihood of developing a new, fully functional corneal endothelial cell layer. AURN001 is expected to replace and repair the corneal endothelial architecture and restore function, which ultimately reestablishes the fluid balance needed to reinstitute corneal clarity and improve vision¹⁶.

Figure 1 Corneal Endothelial Cell Location and Structure with Expected Y-27632 Mechanism of Action

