10.8 Safety Analyses

All safety analyses will be conducted on the Safety Analysis Set. No formal statistical tests of treatment difference are planned.

AEs will be coded using the Medical Dictionary for Regulatory Activities TEAEs (i.e., AEs that begin or worsen in severity after initiation of study drug) will be summarized by treatment arm and overall, in the study eye. Non-ocular TEAEs will also be summarized. Additionally, TEAEs and serious AEs will be summarized in a similar manner by maximum severity and relationship to study drug and the surgical procedure.

Changes from baseline of quantitative measurements (ophthalmic evaluations, laboratory findings) will be summarized by treatment arm and timepoint.

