4 TRIAL DESIGN

4.1 Description of Trial

This is a multicenter, randomized, double-masked, parallel-arm, dose-ranging, Phase 1/2 study of AURN001 in subjects with corneal edema secondary to corneal endothelial dysfunction. The efficacy and safety of AURN001 will be assessed in a clinical trial setting in North America in adult subjects with corneal edema secondary to corneal endothelial dysfunction. Three doses of AURN001 compared with the 2 components of AURN001 separately (*neltependocel* and Y-27632) will be evaluated to assess the contribution of these 2 elements to the efficacy and safety of AURN001.

This trial will enroll approximately 100 subjects in the 5 treatment arms with approximately 20 subjects per arm. A randomized treatment sequence will be assigned. The sponsor will assess the actual enrollment in each arm on an on-going basis throughout the study to maintain a

randomization ratio of 1:1:1:1:1. The sponsor will make adjustments to the randomized treatment sequence and the number of subjects to be treated in each cohort as needed.

The treatment arms are as follows:

[figure not shown]
Table 1 Treatment Assignment Paradigm

Arm	No. of Subjects	Neltependocel Dose	Y-27632 Dose	Endothelial Polishing?
1	20	1.0×10^6	100 μ M	Yes
2	20	5.0×10^5	100 μ M	Yes
3	20	2.5×10^5	100 μ M	Yes
4	20	None	100 μ M	Yes
5	20	1.0×10^6	None	Yes

This study will have a screening period, a surgery/treatment day during which treatment will be administered, and a 12-month observation period. The primary efficacy analysis will be conducted at Month 6. The study will have up to 10 visits with one optional visit: the Screening Visit (Visit 1, -77 days to -7 days); Surgery/Treatment (Visit 2, Day 1); and Follow-up (Visits 3 through 10, Day 2, Week 1, Week 4, and Months 2 (optional), 3, 4.5, 6, 9, and 12, respectively). Unscheduled visits will be allowed, as deemed necessary by the investigator.

This study will be conducted per the schedule shown in Figure 1.

Figure 1 Study Schematic

Assessments can be found in the Schedule of Assessments in Appendix 1.

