4.3 Randomization and Masking

This study will be double-masked and will utilize a randomized treatment sequence model. A computer-generated encrypted read-only randomized treatment sequence schedule will be provided by a biostatistician. The randomized treatment sequence schedule will be managed by unmasked team members responsible for assessing enrollment in each arm to maintain a randomization ratio of 1:1:1:1:1.

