14 SAFETY ANALYSES

14.1 Adverse Events

Adverse events will be coded using Medical Dictionary for Regulatory Activities (MedDRA) version 26.1.

Treatment-emergent adverse events (TEAEs) are defined as any adverse events that occur during or after the Day 1 injections, or any adverse events that are continuous from the screening but worsen during or after the Day 1 injections.

Ocular and non-ocular TEAEs will be summarized separately. Summary of ocular TEAEs will be separated by study eye and non-study eye.

An overall summary including the number of events and the number and percentage of subjects who experienced at least one TEAE will be presented by treatment group and overall. The overall summary will also include at least one serious TEAE, treatment-related TEAE, treatment-related serious TEAE, TEAE leading to subject discontinuation from the study, and TEAE leading to death.

TEAEs will be summarized by System Organ Class (SOC) and Preferred Term (PT). Subjects are counted only once under each SOC or PT for which they have at least one TEAE.

Summaries by relationship to study product, by relationship to study procedure and by maximum severity will also be provided.

Serious TEAEs will not be summarized in table format as it is anticipated number of serious TEAEs will be very limited.

In addition, the following AE summaries will be provided for AEs collected at and after rescue visits:

- Overall summary of TEAE
- TEAE by SOC and PT

For these summaries, denominators to be used for percentage calculation will be number of Rescued subjects.

All AEs will be presented in a subject listing with a flag indicating TEAE and a flag indicating AEs occurred at and after rescue visits. In addition, all serious AEs will be presented in a separate listing.

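### No planned safety table pools the roughly 60 AURN001 or 80 cell-treated subjects, and the SAP drops the protocol's serious-AE breakdown without declaring it

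*SAP*

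**What the plan says.** **Design.** SAP 4.1: "This trial will enroll approximately 100 subjects in the 5 treatment arms with approximately 20 subjects per arm". The comparison is described as "Three doses of AURN001 compared with the 2 components of AURN001 separately". In Table 1, Arms 1-3 receive cells plus Y-27632 at three cell doses, Arm 4 receives Y-27632 without cells, and Arm 5 receives cells without Y-27632. Protocol 4.2 defines the product: "AURN001 is a combination product of allogeneic human corneal endothelial cells" given with Y-27632. Arm 5 is therefore not AURN001 either.

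**Layout of safety tables.** SAP 6.1: "All safety and efficacy summaries will be presented by treatment group and overall, where appropriate, for each study visit". SAP 14.1 (overall TEAE summary), 14.2 (vision loss) and 14.9 (IOP), and Protocol 10.8 (adverse events), follow the same pattern. The Safety Analysis Set is every treated subject, so the overall column spans all five arms. Neither document defines a pooled group, and SAP 7.12 marks subpopulations as not applicable.

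**Purpose of the sample size.** The protocol synopsis bases the size on feasibility and on "adequate size to characterize safety in the study population", without regard to power.

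**Serious events.** Protocol 10.8: "TEAEs and serious AEs will be summarized in a similar manner by maximum severity and relationship to study drug and the surgical procedure". SAP 14.1: "Serious TEAEs will not be summarized in table format as it is anticipated number of serious TEAEs will be very limited". SAP 15 reports that nothing changed from the protocol-stated analyses.

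**The concern.** A reader who asks how often an event occurs after AURN001, or after cell injection, finds no column for that group. The arm columns hold about 20 subjects each, so their intervals are wide. The overall column is larger but answers a different question, because one fifth of it received no cells and two fifths did not receive the combination.

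This matters most for risks that depend on the cells. Protocol 4.4.1 names graft rejection or failure as a product risk and tumor formation as a theoretical risk of cell therapy. For such events, Arm 4 adds subjects to the denominator without the exposure.

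The serious-event point is separate. The protocol plans a summary, the SAP withdraws it because few events are expected, and the SAP section that should record the departure says there is none.

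**Working it through.** **Inputs.** Five arms, about 20 each, about 100 in all (SAP 4.1), with a "randomization ratio of 1:1:1:1:1" (SAP 4.3). There is no power calculation to reproduce. The stated total checks: 5 × 20 = 100.

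**Group sizes.**
- AURN001 (Arms 1-3): 3 × 20 = 60
- Any cells (Arms 1-3 and 5): 4 × 20 = 80
- In the overall column without cells (Arm 4): 20
- In the overall column without AURN001 (Arms 4 and 5): 40

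**Precision.** The two-sided 95% upper limit for zero events in n is 1 − 0.025^(1/n). The one-sided version is 1 − 0.05^(1/n). The last column gives Clopper-Pearson intervals at an observed 10%, an illustrative rate.

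| Group | n | Two-sided upper limit, 0 events | One-sided upper limit, 0 events | 95% CI at observed 10% |
|---|---|---|---|---|
| Single arm | 20 | 16.8% | 13.9% | 2/20: 1.2% to 31.7% |
| AURN001 | 60 | 6.0% | 4.9% | 6/60: 3.8% to 20.5% |
| Any cells | 80 | 4.5% | 3.7% | 8/80: 4.4% to 18.8% |

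**Dilution in the overall column.** Overall rate = 0.8 × (rate in the cell-treated) + 0.2 × (rate in Arm 4). The Arm 4 rate is an assumption, so two values are shown. The 5% and 19% rates have the size of adverse-event rates in Protocol 4.5 and 4.4.1. They illustrate scale and do not imply that those events are caused by the cells.

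| True rate with cells | Overall, Arm 4 rate 0% | Overall, Arm 4 rate 5% |
|---|---|---|
| 5% | 4.0% | 5.0% |
| 10% | 8.0% | 9.0% |
| 19% | 15.2% | 16.2% |

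If an event occurred only with the combination (a further assumption), the overall column would show 60% of its rate: 0.6 × 10% = 6.0%.

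**What can be rebuilt from the arm columns.** The arms are disjoint and SAP 14.1 counts each subject once per SOC or PT, so subject counts can be added. Means and SDs can be recombined from n, mean and SD, apart from rounding. Medians and the Kaplan-Meier estimate of time to rescue (SAP 14.3) cannot be rebuilt from per-arm summaries; they need the subject-level data.

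**Serious events.** SAP 14.1 keeps rows for at least one serious TEAE and at least one treatment-related serious TEAE in the overall summary, by group and overall, and lists all serious AEs. What Protocol 10.8 plans and the SAP omits is the summary of serious AEs by maximum severity and by relationship to drug and procedure.

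**The case against.** The strongest reply is that per-arm columns are what the trial set out to produce. The safety objective (Protocol 5, SAP 3) is worded by cell concentration and by component, in a dose-ranging study with descriptive safety analysis. That stands. A reader might infer that no table estimates the safety of AURN001 or of the cells, or that the secondary objective goes unanswered. The documents do not support either: Arms 1-3 estimate AURN001 at each dose and Arm 5 estimates cells alone, imprecisely.

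A reader might also infer that pooling improves the chance of seeing a rare event. It does not. For an illustrative 3% event, the chance of at least one case in Arms 1-3 is 1 − 0.97^60 = 84%, whether the 60 subjects sit in one column or three. Pooling changes the estimate and interval presented, not what is observed.

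Many listed risks are surgical, and all arms have polishing and injection. For those risks the overall column is informative, and SAP 6.1 uses it only where appropriate. This also stands and limits the dilution argument to cell-related events.

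The any-cell pool mixes groups too. Protocol 4.5 reports meaningfully weaker activity with cells alone, including on need for rescue. This stands for rescue and vision loss.

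SAP 2 permits additional analyses. But SAP 7.1 unmasks the sponsor at Month 6, so a pooling chosen after that would be post hoc.

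On serious events, it would be wrong to read the SAP as removing them from all tables, given the retained rows and listing. SAP 2 also lets the SAP supersede the protocol's methods. That settles which text governs, but it does not make the statement in SAP 15 correct.

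**Conclusion.** The point holds as a modest reporting gap with two parts.

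First, no pooled AURN001 or any-cell safety column is pre-specified, and the only pooled column includes about 20 subjects without cells and about 40 without AURN001. Pooling would lower the zero-event upper limit from 16.8% to 6.0% (AURN001) or 4.5% (any cells). The overall column understates a cell-related rate by one fifth if Arm 4 has no events, and by one tenth for a 10% event if Arm 4 has 5%. These figures assume arms of exactly 20. The pooled intervals describe an average over the doses given, not the risk at any one dose.

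Second, omitting the serious-AE summary by severity and relationship is an undeclared departure from Protocol 10.8. This needs no assumption, and it stands whatever is decided about pooling.

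**What to change.** - **Columns.** In SAP 6.1, keep the five arm columns and define two pooled columns: AURN001 (Arms 1-3) for the safety tables, and any neltependocel (Arms 1-3 and 5) for TEAEs.
- **Intervals.** Give exact 95% CIs in the pooled columns for key binary outcomes: selected TEAEs, vision loss of 15 letters or more, rescue, and the IOP thresholds in SAP 14.9.
- **Continuous and time-to-event summaries.** Add a pooled AURN001 summary for IOP change and for Kaplan-Meier time to rescue.
- **Caution.** If the any-cell pool is also shown for rescue or vision loss, add a note that cells alone may perform differently (Protocol 4.5).
- **Serious events.** Restore the summary of Protocol 10.8, whatever the count, and correct SAP 15. If the sponsor prefers to keep only the overall rows and the listing, SAP 15 must state that change and the reason.
- **Timing.** Make the change before the Month 6 unmasking. If that has passed, label the pooled columns as added afterwards.

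The cost is SAP wording and a little programming, with no new data. Pooling can mask a dose trend or a cells-alone difference, but the retained arm columns still show both.

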6.2 Treatment Comparison

For the purpose of statistical comparison, each combination arm will be compared to each component. That is the 3 different concentrations of *neltependocel* in combination with Y-27632 (i.e., AURN001) will be compared to *neltependocel* alone, and to Y-27632 alone.

Two components will also be compared to each other. That is *neltependocel* alone compared to Y-27632 alone.

6.3 Definition of Baseline

Baseline measurements are the last measurement prior to the study drug injection on Day 1. Change from baseline values will be calculated as follow-up visit minus baseline visit.

6.4 Definition of Study Day

Start day of study treatment is the day of the first dose of study treatment, i.e. Day 1 as defined in the protocol.

The study day for assessments occurring on or after the start of study treatment (e.g., adverse event onset) will be calculated as:

Study day = Date of the assessment/event - start date of study treatment + 1.

The study day for assessments occurring prior to the first dose of study treatment (e.g., medical history) will be negative and calculated as:

Study day = Date of the assessment/event - start date of study treatment.

The study day will be displayed in all relevant data listings.

6.5 Unscheduled visits

All by-visit assessments will be summarized and presented using the nominal visit provided in the data. Programmatic visit windows will not be used, unless otherwise specified.

Unscheduled visits will be used in the determination of baseline. All data, including unscheduled visits, will be present in data listings.

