8.4.12 Unscheduled Visits

An unscheduled visit may be performed during the course of the trial in order to ensure subject safety.

All procedures performed at an unscheduled visit will be recorded in the source documents and on the Unscheduled Visit eCRF pages.

Evaluations that may be conducted at an Unscheduled Visit may include:

- BCVA assessment (through phoropter)
- Slit Lamp Biomicroscopy
- Slit Lamp Photography
- Assessment of AEs
- Assessment of concomitant medications and/or treatments
- Any other assessments needed in the judgment of the investigator

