14.2 Vision Loss

The number and percentage of subjects who have loss from baseline in BCVA ≥ 15 letters will be summarized using counts and percentages at each post-baseline visit by treatment group and overall.

The best corrected visual acuity will be presented in a listing.

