14.9 Intraocular Pressure

The observed and change from Baseline in IOP will be summarized for study eye and non-study eye separately using continuous descriptive statistics at each post-baseline visit by treatment group and overall.

The number and percent of subjects with a ≥ 10 mmHg increase from baseline and the number and percent of subjects with a ≥ 30 mmHg observed value will be presented.

Post-baseline IOP data will be presented in a listing, along with flags indicating a ≥ 10 mmHg increase from baseline and a ≥ 30 mmHg observed value.

IOP data will be presented in a listing.

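### A BCVA loss of 15 letters or more seen only at an unscheduled visit has no place in the planned vision-loss table, and for the IOP thresholds the SAP leaves the question open

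*SAP*

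**What the plan says.** **Visit handling.** SAP 6.5 sets the rule for tables: "All by-visit assessments will be summarized and presented using the nominal visit provided in the data". It adds: "Programmatic visit windows will not be used, unless otherwise specified". On unscheduled data it says: "Unscheduled visits will be used in the determination of baseline. All data, including unscheduled visits, will be present in data listings". The general convention in SAP 6.1 is: "All safety and efficacy summaries will be presented by treatment group and overall, where appropriate, for each study visit".

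**Vision loss.** A loss of 15 letters or more is a named safety evaluation (Protocol 6.2.2, SAP 4.2.2). Under SAP 14.2 the number and percentage of subjects with such a loss "will be summarized using counts and percentages at each post-baseline visit by treatment group and overall". The BCVA listing has no planned flag for the threshold.

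**IOP.** SAP 14.9 first describes by-visit descriptive statistics. A separate paragraph then gives two threshold counts. The first is for a rise: "The number and percent of subjects with a ≥ 10 mmHg increase from baseline". The second is for a reading of 30 mmHg or higher. Neither mentions a visit. The IOP listing flags both thresholds.

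**Unscheduled visits.** Protocol 8.4.12 gives their purpose: "An unscheduled visit may be performed during the course of the trial in order to ensure subject safety". BCVA is the first evaluation it lists, and the schedule in Appendix 1 marks tonometry as optional there.

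**Neighbouring rules.** SAP 7.9 keeps readings at and after rescue visits out of the tables, apart from adverse events, which are summarised separately. Protocol 9.3 says that clinical findings linked to lack of efficacy are not adverse events.

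**The concern.** Unscheduled visits are where an acute problem is most likely to be seen first, because they are held for safety. A threshold table built only from scheduled visits can miss a subject who crossed the threshold between them. A set of by-visit rows also cannot show how many different subjects were ever affected.

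This bears on the trial's stated purpose. SAP 7.3 gives no power target. The study is meant to supply initial estimates and safety information, in arms of about 20. At that size, one subject with a severe vision loss is a visible part of an arm's safety profile.

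**Working it through.** The plan gives no figure on this point, so there is nothing to reproduce. The check follows single readings through the rules, then gives the size of one missed subject.

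**Step 1: a BCVA loss found at an unscheduled visit.** Take a hypothetical eye seen unscheduled on Day 15 with a 20-letter loss. The next scheduled BCVA is Day 30 (Appendix 1).

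- *Loss persists to Day 30, no rescue:* counted in the Day 30 row.
- *Loss resolves by Day 30:* the Day 15 value has no scheduled nominal visit, and no window moves it to one. No any-time row exists, so the eye is not counted.
- *Eye is rescued before Day 30:* the Day 30 reading falls after rescue and is removed by SAP 7.9. The Day 15 reading predates rescue, so SAP 7.9 does not remove it, but it still has no row. The eye is never counted as a vision loss.

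The line-loss summary in SAP 13.2 is also by visit, so it does not fill the gap. The adverse event tables may not fill it either: a loss put down to treatment failure can fall under Protocol 9.3.

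**Step 2: an IOP spike found at an unscheduled visit.** Two readings of SAP 14.9 are open.

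- *Per subject, any time:* the threshold paragraph has no visit qualifier, so an unscheduled value could count.
- *By visit:* the SAP 6.1 default applies where appropriate, and an unscheduled value has no scheduled row.

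The text does not settle which is meant.

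**Step 3: room for events between scheduled visits.** Days and windows are from Appendix 1. The longest gap is the latest day of the later visit minus the earliest day of the earlier one.

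- BCVA: none scheduled from screening to Day 30.
- IOP, Day 8 to Day 30: 30 − 8 = 22 days; longest 37 − 8 = 29.
- Both, Day 30 to Day 90 with the optional visit skipped: 90 − 30 = 60; longest 60 + 7 + 7 = 74.
- Both, Day 180 to 270 and Day 270 to 360: 90 each; longest 90 + 14 + 14 = 118.

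**Step 4: size of one missed subject.** With n = 20, one subject is 1/20 = 5 percentage points. Exact (Clopper-Pearson) 95% limits are shown for scale only, since the SAP plans none for safety tables. For x = 0 the upper limit is 1 − 0.025^(1/n), which gives 16.8% for n = 20 and 3.6% for n = 100.

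| Count | Percent | 95% interval |
|---|---|---|
| 0/20 | 0% | 0 to 16.8% |
| 1/20 | 5% | 0.1 to 24.9% |
| 2/20 | 10% | 1.2 to 31.7% |
| 0/100 | 0% | 0 to 3.6% |
| 1/100 | 1% | 0.03 to 5.4% |

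These rows show what one or two extra subjects would do. They are not a forecast, because the documents give no rate of events seen only at unscheduled visits.

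**The case against.** The strongest reply is that SAP 6.5 does not confine unscheduled data to listings. It says that all data will be listed, not that unscheduled data will appear nowhere else. Where the SAP wants a listings-only rule, as for post-rescue data in SAP 7.9, it says so outright. A table row labelled as unscheduled is not ruled out. This stands: exclusion from the vision-loss table follows from reading SAP 6.1, 6.5 and 14.2 together, and is not written anywhere.

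Second, an event can surface elsewhere. Any adverse event from Day 1 to Month 12 is recorded (Protocol 9.4.1), and SAP 14.1 tabulates treatment-emergent events without regard to visit. An IOP spike recorded as an adverse event therefore does reach a table, though without the 10 or 30 mmHg thresholds. A rescued eye appears in the rescue summaries of SAP 14.3, though not as a vision loss. A loss that persists unrescued is counted at the next scheduled visit. All of this narrows the gap without closing it.

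Third, a by-visit percentage describes subjects at that visit, and leaving out unscheduled readings does not bias it. This also stands. What the plan lacks is a different summary, the proportion ever affected.

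Fourth, an any-time row over all readings would bring in values after keratoplasty and conflict with SAP 7.9. That is correct, and the fix has to be limited to readings before rescue.

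**Conclusion.** The point holds for BCVA and, as an ambiguity, for IOP. On the natural reading, a loss of 15 letters or more seen only at an unscheduled visit has no place in the vision-loss table. The most serious case is an eye that loses vision at such a visit and is rescued before the next scheduled one. This assumes that the reading comes from a visit before the rescue visit, and that the analyst adds no unscheduled or any-time row on their own initiative.

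The size is 5 percentage points per missed subject in a 20-subject arm. The number of such subjects is unknown.

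A reader might infer more, but the documents do not support it:

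- *That IOP spikes are certainly left out of the threshold counts.* SAP 14.9 allows an any-time reading.
- *That the 7%, 15% and 16% for raised IOP in Protocol 4.4.1 measure the loss.* They are occurrence figures for reported risks in prior trials, not rates of crossing 10 or 30 mmHg, and events of that kind would reach the adverse event tables.
- *That the comparison between arms is distorted.* Unequal loss is possible, but nothing in the documents shows it.

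The trial is descriptive and the listings are complete, so this is a worthwhile improvement to the safety summaries and does not undermine the primary analysis.

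**What to change.** 1. In SAP 14.2, add by arm the number and percent of subjects with a BCVA loss of 15 letters or more at any post-baseline assessment before rescue, scheduled or unscheduled. The denominator is all treated subjects (the Safety Analysis Set).
2. In SAP 14.9, add the same row for the 10 mmHg rise and for the 30 mmHg value, and state whether the existing threshold counts are by visit.
3. In SAP 6.5, state that unscheduled post-baseline values count in these rows.
4. Keep the by-visit rows and the SAP 7.9 rule unchanged.

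The cost is a few lines of SAP text and one extra row per threshold, from data already collected. The reported rates may come out slightly less favourable.
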